6.5.1 Rescue Medicine

The Sponsor will not supply any rescue medication. The site will use standard and locally acceptable rescue medications in line with current box labeling, as appropriate. However, the risk-benefit of use of such medications must be assessed case-by-case by the Investigator or his team. The date and time of rescue medication administration as well as the name and dosage regimen of the rescue medication must be recorded.

6.6 DOSE MODIFICATION

6.6.1 General rules

Cycle delay (ie, delay of IMP for Cycle 2 and 3), dose delay, or dose omission (ie, omission within a cycle) are permitted in case of toxicity.

Administration of the IMP will be discontinued in the event of a TEAE that persists despite appropriate dose modifications or any other AE that, in the opinion of the Investigator, warrants discontinuation.

There will be no dose reduction for isatuximab.

Any changes to IMP administration must be recorded in the eCRF.

6.6.2 Dose delay and dose omission

Within a cycle, the treatment window is ± 1 day for each of the weekly administrations and ± 2 days for each of the Q2W administrations. Within a cycle, a dose is deemed to have been delayed if the treatment is ≥ 2 days beyond the theoretical day of treatment for weekly dose, or ≥ 3 days beyond the theoretical day of treatment for Q2W dose. The reason for dose delay must be captured. The participant will receive the next infusion/cycle after recovery from the AE.

If infusion has been delayed within a cycle, the next dose of IMP should be administered at the planned time interval between the 2 administrations (eg, if Cycle 1 Day 15 administration was administered on Day 17, the planned Day 22 should be administered on Day 24 ± 1 day).

Participants may have dose delay, cycle delay, or dose omission if an AE occurs and does not recover according to the following rules:

- In Cycle 1 (for weekly administration) if an AE occurs and the participant does not recover on the day of planned infusion or within the following 3 days, infusion of isatuximab (Day 8, Day 15, or Day 22) may be omitted.
- In Cycles 2 and 3:
 - For Day 1 infusions: If an AE occurs and the participant does not recover on the day of planned infusion, the cycle may be delayed up to a maximum of 2 weeks.
 - For Day 15 infusions: If an AE occurs and the participant does not recover on the day of planned infusion or within the following 7 days, infusion of isatuximab may be omitted.
- If the AE is not recovered within 14 days:
 - IMP may be delayed up to 56 days.
 - After a cycle delay of >14 days and ≤ 56 days, it is per Investigator's decision to restart the treatment or the IMP that is omitted, if a clear benefit from therapy is observed and after consultation with the Medical Monitor.
 - The IMP must be definitively permanently discontinued if the dose/cycle delay is longer than 56 days.

6.6.3 General guidelines for the management of adverse events

Guidelines for isatuximab dose modifications and treatment discontinuation due to hematological and non-hematological AEs in general are outlined in [Table 5](#).

The final decision will be per Investigator's judgment for the best interest of the participant.

Table 5 - General management guidelines for adverse events

Adverse Event (NCI-CTCAE version 5.0 criteria)	Management of Isatuximab	Action and Guidelines
Hematological AE		
Grade 1, 2, 3	No change in dose	Participant should be given supportive care and monitored closely.
Grade 3 Thrombocytopenia lasting >7 days or associated with bleeding	Delay the dose/cycle until bleeding is controlled and platelet >50 000/mm ³ . Restart treatment with the same dose and schedule.	
Grade 4	Delay the dose/cycle until ANC >1000/mm ³ , or platelet >50 000/mm ³ , or hemoglobin >8 g/dL. Restart treatment with the same dose and schedule. Grade 4 lymphopenia: no change in dose.	Participant should be given supportive care and monitored closely. Permanent discontinuation should be considered if AE does not resolve/recover within 56 days of last infusion.
Febrile neutropenia and/or neutropenic infection	Delay the dose/cycle until fever and infection recovered and ANC >1000/mm ³ . Restart treatment with the same dose and schedule.	
Non-hematological AE		
Grade 1	No change in dose	Not applicable
Grade 2	Delay the dose/cycle until improves to Grade ≤ 1 or baseline. Restart treatment with the same dose and schedule.	If the treatment interruption is >14 days, before restarting the treatment, Investigator must discuss with the Sponsor; if it is determined that it is for the best interest of the patient, treatment may be restarted.
Grade 3	Delay the dose/cycle until improves to Grade ≤ 1 or baseline. Restart treatment with the same dose and schedule	
Grade 4	Permanently discontinue treatment for treatment related AEs. For treatment unrelated AEs, delay the dose/cycle until improves to Grade ≤ 1 or baseline. Restart treatment with the same dose and schedule.	If the interruption is longer than 56 days, the treatment must be definitively discontinued
Infusion Reaction: see Table 6 for management guideline		

Abbreviations: AE = adverse event, ANC = absolute neutrophil count, CTCAE = common terminology criteria for adverse events, IV = intravenous, NCI = National Cancer Institute

Guidance in case of hepatitis B reactivation occurring under study treatment

In case of viral reactivation during study treatment (greater than $1\log_{10}$ IU/mL increase in HBV DNA or reappearance of HBsAg or detection of HBV DNA in patients with resolved infection*), study treatment will be held and specialist should be consulted for initiation of anti-viral treatment and monitoring of the patient. Re-start of study treatment should be agreed between sponsor, investigator and specialist (hepatologist) if controlled infection. Close monitoring of ALT and AST approximately every month (may coincide with the next scheduled blood sampling ± 7 days) up to study treatment discontinuation. HBV DNA to be done as per Investigator's or specialist advice.

** Previous known history of acute or chronic hepatitis B or the presence of total anti-HBc with/without anti-HBs; HBsAg negative; undetectable serum HBV DNA; normal ALT levels.*

6.6.4 General guidelines for the management of infusion reactions

Participants should routinely receive premedications prior to isatuximab infusion as detailed in [Section 6.1](#) to reduce the risk and severity of IRs commonly observed with mAbs.

Infusion reactions typically occur within 24 hours from the start of the infusion.

If an IR is observed, participants must also be informed of the potential risk of recurrent similar reactions at subsequent infusions. The guidelines for management of IRs are summarized in [Table 6](#).

Participants may receive additional medication per the judgment of the Investigator. Additional recommended medications are: diphenhydramine 25 mg IV (or equivalent) and methylprednisolone 100 mg IV (or equivalent).

Participant who experience Grade 2 IRs, or first/second Grade 3 IR, may resume isatuximab infusion after temporary interruption, under close monitoring and with therapy as needed.

Once the Grade 2 IR or first/second Grade 3 IR has improved or resolved according to [Table 6](#), the infusion may be restarted as follows at the Investigator's discretion:

- **First infusion:** Infusion could be restarted at one-half (12.5 mL/hour) of the initial infusion rate when the IR improves to Grade ≤ 1 . If symptoms do not recur after 30 minutes, the infusion rate may be increased by 25 mL/hour increments every 30 minutes, until the total volume is infused or reaching 150 mL/hour, whichever is earlier.
- **Second infusion:** Infusion could be restarted at one-half (25 mL/hour) of the initial infusion rate when the IR improves to Grade ≤ 1 . If symptoms do not recur after 30 minutes, the infusion rate may be increased by 50 mL/hour increments every 30 minutes, until the total volume is infused or reaching 200 mL/hour, whichever is earlier.
- **Third and subsequent infusions:** Infusion could be restarted at one-half (100 mL/hour) of the initial infusion rate when the IR improves to Grade ≤ 1 . If symptoms do not recur

after 30 minutes, the infusion rate may be increased by 50 mL/hour increments every 30 minutes, until the total volume is infused or reaching 200 mL/hour, whichever is earlier.

Participants with Grade 3 IR (third Grade 3, or do not fulfil criteria to restart infusion as per **Table 6**) or Grade 4 IR must permanently discontinue the treatment with isatuximab.

Grade 3 or higher IRs for isatuximab must be reported as adverse event of special interests (AESIs) (see [Section 8.3](#)). Study personnel should consult the Medical Monitor for further guidance regarding retreatment of participants with IRs and regarding issues of premedication management (eg, alternative medications for participants allergic or intolerant to premedication agents), or to determine if locally used equivalent medications are acceptable.

Table 6 - Management guidelines for infusion reaction

Infusion related reaction grading (NCI-CTCAE version 5.0 criteria)	Recommendation
Grade 1 Mild transient reaction; infusion interruption not indicated; intervention not indicated.	Continuation of isatuximab infusion is per the judgment of the Investigator following close direct monitoring of the participant's clinical status.
Grade 2 Therapy or infusion interruption indicated but responds promptly to symptomatic treatment (eg, antihistamines, NSAIDS, narcotics, IV fluids); prophylactic medications indicated for ≤ 24 hours).	Stop isatuximab infusion. Give additional medication(s) with IV diphenhydramine 25 mg (or equivalent) and/or IV methylprednisolone 100 mg (or equivalent), and/or other supportive care as needed. Isatuximab^a may be resumed only after participant recovery, with reduced infusion rate and with close monitoring.
Grade 3 Prolonged (eg, not rapidly responsive to symptomatic medication and/or brief interruption of infusion); recurrence of symptoms following initial improvement; hospitalization indicated for clinical sequelae.	Stop isatuximab infusion. Give additional medication(s) with diphenhydramine 25 mg IV (or equivalent) and/or IV methylprednisolone 100 mg (or equivalent) and/or epinephrine as needed until resolution of the AE or until the AE improves to Grade 1. Only then, the infusion may be restarted at the Investigator's discretion: if so, the infusion rate should be half of the initial infusion rate, and it may be increased subsequently, at the Investigator's discretion. If the severity of an infusion-related AE returns to Grade 3 after the restart of the infusion, the same procedure described above may be repeated at the Investigator's discretion. If a Grade 3 infusion-related AE occurs for a 3 rd time, treatment with isatuximab will be definitively discontinued for that participant. If symptoms do not resolve rapidly, do not improve after interruption of the isatuximab infusion, they recur after initial improvement with appropriate medications, or they require hospitalization, treatment with isatuximab should be definitively discontinued. Report as AESI.

Infusion related reaction grading (NCI-CTCAE version 5.0 criteria)	Recommendation
Grade 4 Life-threatening consequences; urgent intervention indicated.	Definitive discontinuation of isatuximab. Give additional premedication with diphenhydramine 25 mg IV (or equivalent) and/or IV methylprednisolone 100 mg (or equivalent) and/or epinephrine as needed. Report as AESI.

Abbreviations: AESI = adverse event of special interest, CTCAE = common terminology criteria for adverse events, IR = infusion reaction, IV = intravenous, NCI = National Cancer Institute, NSAIDS = nonsteroidal anti-inflammatory drugs.

a Isatuximab: the infusion should be completed within 16 hours from the end of infusion preparation or a new infusion should be prepared with the remaining dose to be administered the same day.

6.6.5 Retreatment of participants

The participants must have recovered to National Cancer Institute (NCI) common terminology criteria for adverse events (CTCAE) Grade ≤ 1 or to the baseline status before initiation of the next cycle at the same dose level.

In the event of an AE causing a delay, in order for participants to be retreated, see [Section 6.6.1](#) to [Section 6.6.4](#) for recommendations.

6.7 INTERVENTION AFTER THE END OF THE STUDY

The IMP will not be provided after the end of the treatment period. The participant's treatment after study discontinuation will be at the discretion of the treating physician.

For participants who received isatuximab treatment and subsequently proceed to solid organ transplantation, it is recommended to include the following as part of the post-transplant immunosuppression regimen:

- Anti-thymocyte globulin (rabbit) as indicated for prophylaxis of acute rejection.
- Steroids during maintenance phase, with tapering if applicable.

7 DISCONTINUATION OF STUDY INTERVENTION AND PARTICIPANT DISCONTINUATION/WITHDRAWAL

Refer to [Section 7.1](#) and [Section 7.2](#) for details regarding discontinuation of study intervention and participant discontinuation.

7.1 DISCONTINUATION OF STUDY INTERVENTION

7.1.1 Definitive discontinuation

In rare instances, it may be necessary for a participant to permanently discontinue study intervention. If study intervention is permanently discontinued (except in the case of discontinuation due to transplantation), the participant will remain in the study to be evaluated as per the assessments planned for site visit FUP. See the SoA ([Section 1.3](#)) for data to be collected at the time of discontinuation of study intervention.

The IMPs should be continued until end of treatment period whenever possible.

In case the IMP is stopped, it should be determined whether the stop can be made temporarily. Any IMP discontinuation must be fully documented in the eCRF.

Pregnancy will lead to definitive treatment discontinuation in all cases.

Treatment with the IMP should be discontinued in any of the following cases:

- At the participant's request, at any time and irrespective of the reason (participant's decision), or at the request of their legally authorized representative without any effect on their care. "Legally authorized representative" is considered to be an individual or judicial or other body authorized under applicable law to consent on behalf of a prospective patient to the patient's participation in the procedure(s) involved in the research.
- If, in the Investigator's opinion, continuation of the IMP would be detrimental to the participant's well-being, such as:
 - unacceptable AE,
 - poor compliance to the study protocol,
 - any other reason such as intercurrent illness that prevents further administration of IMP (will be specified).
- Participant is lost to follow-up.
- Completion of the 3 cycles of treatment period.

See the SoA for data to be collected at the time of intervention discontinuation and follow-up and for any further evaluations that need to be completed.

Any abnormal laboratory value or ECG parameter will be immediately rechecked for confirmation (per Investigators discretion) before making a laboratory/ECG abnormality-driven decision of definitive discontinuation of the IMP for the concerned participant.

Handling of participants after definitive intervention discontinuation

Participants will be followed-up according to the study procedures specified in this protocol up to the scheduled date of study completion, or up to recovery or stabilization of any AE to be followed-up as specified in this protocol, whichever comes last.

In the case of participants discontinuing IMP during treatment period due to transplantation, the participants should complete an E/D visit (30 ± 7 days after last IMP) if clinically feasible, and proceed to extended FUP.

All cases of definitive intervention discontinuation must be recorded by the Investigator in the appropriate pages of the eCRF when considered as confirmed.

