Prior/concomitant/post medication ^m	X	←=====→								X	X	X	See Section 6.5				
Participant/Transplant (if applicable) Status	X ⁿ	X ⁿ								X ^o	X ^o						

Abbreviations: ADA = anti-drug antibody, AE = adverse event, CMV = cytomegalovirus, cPRA = calculated panel reactive antibodies, D = Day, EBV = Epstein-Barr virus, ECG = electrocardiogram, E/D = early discontinuation, FUP = follow-up period, HBV = hepatitis B virus, hCG = human chorionic gonadotropin, HCV = hepatitis C virus, HIV = human immunodeficiency virus, HLA = human leukocyte antigen, ID = identification number, IMP = investigational medicinal product, MFI = mean fluorescence intensity, PK = pharmacokinetics, SAB = single antigen bead, SoA = Schedule of Activities, SAE = serious adverse event, WOCBP = women of childbearing potential.

- a Week 1 visit for site visit FUP will occur 15 days after Cycle 3 Day 15 (± 7 days), or 15 (± 7 days) after the last dose of IMP if participant discontinued IMP. Depending on local arrangements and preference of the Investigator, site visit FUP procedures may be performed at the study site or at the participant's home by a health care professional. Study procedures not performed at the study site must also be documented in the source documents and recorded in the appropriate pages of the eCRF by the study site.
- b For E/D, study procedures will be performed 30±7 days after last IMP administration if discontinued study during treatment period, or within 30 days if discontinued during site visit FUP. Participants who discontinued IMP but remain on the study and proceed to complete site visit FUP do not need to complete E/D. Participants who wish to proceed to transplantation when a compatible donor becomes available while on study must discontinue IMP immediately, and complete an E/D visit prior to transplantation if clinically feasible, and proceed to extended FUP.
- c In addition to the phone calls every 90 days, study site will collect information per the SoA throughout the extended FUP.
- d Vital sign assessment includes blood pressure, pulse rate, temperature, and respiratory rate. During the treatment period, vital signs should be obtained prior to start of each IMP infusion, 1 hour after start of infusion, at the end of infusion, and during the infusion if clinically indicated.

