The study will have a screening period of up to 28 days, a treatment period of up to 12 weeks, a site visit follow-up period (FUP) of up to 26 weeks, and an extended FUP which include telephone contacts every 90 days and information collection until study cut-off, death, or lost to follow-up. The study cut-off is planned at 26 weeks after the last participant completes the treatment period, or when the last ongoing participant is lost to follow-up, whichever is earlier. The Sponsor (Sanofi) may choose to extend the study cut-off date depending on the enrollment rate observed to facilitate adequate follow-up data collection. Participants who wish to proceed to transplantation when a compatible donor becomes available while on study must discontinue IMP immediately, complete an early discontinuation (E/D) visit prior to transplantation if clinically feasible, and proceed to extended FUP. The study duration that involves site visit per participant (ie, screening, treatment, site visit FUP) will be approximately 42 weeks. The study duration including extended FUP per participant will be approximately 78 weeks (depending when the participant is enrolled).

Treatment period: The cycle duration is 28 days and a complete treatment period is comprised of 3 cycles of IMP treatment. Participants will continue treatment until receiving 3 cycles of IMP, unacceptable AE per Investigator's judgment, or participants' decision to stop the treatment.

Site visit FUP: Participants completing the treatment period and who are able to remain on study will return to the study sites for study procedures.

Extended FUP: The following participants will be followed-up every 90 days by phone calls, until study cut-off date, death, or lost to follow-up, whichever comes first:

- Participants who completed or discontinued from site visit FUP
- Participants who proceed to transplantation during treatment period or site visit FUP.

During extended FUP, specified information per protocol will also be collected by study site (see protocol section 1.3).

Below figures show the study schema and duration of study period:

Figure 1 - Graphical study design

[figure not shown]
[figure not shown]

Figure 2 - Duration of study period (per participant)

Details on schedule of activities (SoA) are provided in protocol section 1.3.

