1.2.1 Estimands

Primary estimand defined for the main efficacy endpoint is summarized in below [Table 2](#).

Table 2 - Summary of primary estimand for main efficacy endpoint

Endpoint Category (estimand)	Estimands			
	Endpoint	Population	Intercurrent event(s) handling strategy	Population-level summary (Analysis and missing data handling)
Primary efficacy objective: Phase 2: To evaluate the efficacy of isatuximab in desensitization of patients awaiting kidney transplantation				
Primary efficacy endpoint (Estimand 1)	Response rate	Efficacy-evaluable	Interruption/discontinuation of study intervention: Response rate will be analyzed regardless of intervention discontinuation (treatment policy)	Response rate, defined as proportion of participants meeting at least one of the predefined desensitization efficacy criteria, from baseline up to 26 weeks after treatment period and two-sided 95% confidence intervals using the Clopper-Pearson method (1)

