4.3.2 Main analytical approach

The primary efficacy analysis is based on a treatment policy estimand introduced in [Section 1.2.1](#).

This primary estimand is defined according to the following attributes:

- The endpoint is RR, as defined in [Section 4.3.1](#).
- The treatment condition of interest is isatuximab
- The analysis population is the efficacy-evaluable population (defined in [Section 3](#))
- The study intervention interruption/discontinuation intercurrent event will be handled with the treatment policy strategy. RR will be assessed based on the 3 criteria irrespective of study intervention interruption/discontinuation.
- Population-level summary will be RR, defined as the proportion of participants meeting at least one of the predefined desensitization efficacy criteria (refer to [Section 4.3.1](#)), along with and two-sided 95% confidence intervals using the Clopper-Pearson method.

Proportion of participants meeting each criterion will also be tabulated.

Calculation details and examples on RR criteria 1 and 2 are provided in Appendix 4, [Section 5.4.2](#) (DESENSITIZATION response criteria).

For RR criterion 3, elimination of anti-HLA-antibody will be determined for each applicable molecular specificity.

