4.4.2 Supportive secondary endpoints

4.4.2.1 Definition of endpoints

The following secondary endpoints in the Phase 2 portion of the study are defined below, with the exception of PK parameters and immunogenicity/ADA against isatuximab which are described in [Section 4.8.1](#) and [Section 4.8.2](#), respectively:

DoR per central laboratory assessment

DoR (based on central laboratory assessment): defined as time from laboratory sample collection date used in determining a participant to be a responder up to the laboratory sample collection date when participant is no longer meeting any response criterion (ie, non-responder) or the date of death due to any cause, whichever occurs first.

For participants with ongoing response at the time of the analysis, DoR will be censored at the date of the last available laboratory assessment showing response. Non-responders will be excluded in the DoR summaries.

For responders meeting more than 1 criterion, DoR will be calculated from: [(earliest of start dates) up to (latest of end dates) + 1] across any response criteria durations.

For responders having multiple DoRs within the same criterion but with gaps, only the 1st DoR (or 1st set of DoRs for those meeting more than 1 criterion) will be summarized. A sensitivity analysis may be performed using the longest DoR (in lieu of 1st DoR), if applicable.

Proportion of participants and duration achieving target cPRA per local laboratory assessment (using OPTN-calculated and using locally reported cPRA values)

Proportion of participants achieving target cPRA: will be summarized separately for cPRA values, based on OPTN calculator and based on locally reported values

Duration of achieving target cPRA: defined as time from laboratory sample collection date of achieving target cPRA the first time up to the laboratory sample collection date when no longer achieving target cPRA or the date of death due to any cause, whichever occurs first.

Participants who retain their target cPRA values will be censored at the date of the last available laboratory assessment achieving their target cPRA. Participants who do not achieve target cPRA will be excluded from the analysis.

For participants with multiple durations (with gaps), only the 1st duration will be summarized. A sensitivity analysis may be performed using the longest duration (in lieu of the 1st duration), if applicable.

Refer to [Section 5.4.2, Table 8](#) for a table of target cPRA.

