4.4.2.2 Main analytical approach

All secondary efficacy endpoints (if applicable) during Phase 2 will be summarized descriptively and presented by cohort. Categorical variables (eg, rates and proportions) will be tabulated via frequency distributions (ie, number and percents). Continuous variables (eg, change from baseline) will be summarized by providing the number of observations (n), mean, median, SD, minimum, and maximum.

DoR and other time to event variables will be analyzed using the Kaplan-Meier method (ie, median and associated 95% confidence interval). No hypothesis/significance testing will be performed.

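### Protocol 7.1.1 times the transplant early-discontinuation visit at 30 ± 7 days after last dose, the rest of the plan puts it before surgery, and the SAP does not exclude post-transplant samples (minor)

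*Protocol*

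**What the plan says.** Protocol 7.1.1 has a sentence only for participants who stop IMP during the treatment period because of transplantation. It times their E/D visit at 30 ± "7 days after last IMP) if clinically feasible, and proceed to extended FUP". It does not say that the visit must come before surgery.

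For the same participants, SoA footnote b says they "complete an E/D visit prior to transplantation if clinically feasible, and proceed to extended FUP". The synopsis and Protocol 4.1 agree, and SAP 1.1 says they "complete an early discontinuation (E/D) visit prior to transplantation if clinically feasible, and proceed to extended FUP". Footnote b also contains the 30 ± 7-day timing, but as the general rule for those who leave the study during treatment. Section 7.1.1 itself points sites to the schedule: "See the SoA for data to be collected at the time of intervention discontinuation and follow-up".

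The SoA places a central cPRA and single-antigen-bead draw at E/D and none in extended follow-up.

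On the analysis side, SAP 4.3.1 takes response from central assessments between baseline and 26 weeks after treatment. SAP 4.3.2 adds that "RR will be assessed based on the 3 criteria irrespective of study intervention interruption/discontinuation". Under SAP 4.4.2.1, DoR ends at loss of response or death. For ongoing responders, "DoR will be censored at the date of the last available laboratory assessment showing response". Transplantation appears in neither rule.

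**The concern.** The two timings often cannot both be met. A site that follows 7.1.1 may skip the pre-transplant draw, which cannot be recovered later, and take the sample after surgery instead. Because extended follow-up has no central draw, that E/D sample is the participant's last.

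The ban on immunosuppression in Protocol 6.5 ends at transplantation, and Protocol 6.7 then recommends anti-thymocyte globulin and steroids. A sample drawn afterwards does not reflect isatuximab alone. As the SAP rules stand, it could still create a response, extend a DoR or end one.

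**Working it through.** The plan gives no figure of its own on this point, so the check is schedule arithmetic plus a bound on frequency.

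**Inputs**
- Infusions (Protocol Table 1 and SoA), on schedule: Days 1, 8, 15, 22, 29, 43, 57, 71, eight in all.
- Section 7.1.1 window: last dose + 23 to last dose + 37 days.
- Scheduled central samples: Days 1, 29 and 57, then every 4 weeks in site-visit follow-up. Follow-up Week 1 is Day 71 + 15 ± 7 = Day 79–93.
- Efficacy-evaluable: at least 75% of planned cumulative doses (SAP 3).
- Waiting time (Protocol 2.1.1): overall US median 4 years. Sensitized patients often exceed 5 years; a 5-year median is used as an assumed second case.

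**1. Can both timings be met?** In Cycles 2 and 3 the call comes 0 to 14 days after the last dose. Window opening minus call = 23 − 14 = 9 days up to 23 − 0 = 23 days. In Cycle 1 (weekly dosing) it is 23 − 7 = 16 up to 23 days. Both timings are met only if surgery falls on or after day 23 from the last dose.

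**2. Who reaches the efficacy analysis?** 0.75 × 8 = 6 infusions, so only stops after dose 6 or dose 7 count. After dose 8 there is nothing left to discontinue.

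| Stop after | Last dose | Call | 7.1.1 window | Share of dose (mg/kg) |
|---|---|---|---|---|
| Dose 6 | Day 43 | Day 43–57 | Day 66–80 | 60/80 = 75.0% |
| Dose 7 | Day 57 | Day 57–71 | Day 80–94 | 70/80 = 87.5% |

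Together the calls span 28 days (Day 43–71). If cumulative dose is counted in mg/kg, as SAP 4.7.1.2 defines it, a dose-6 stop sits exactly on the 75% limit. Any shortfall then removes it and leaves 14 days.

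**3. Expected transplants in that span, per 12 participants.** Constant hazard h = ln 2 / (median × 365.25); expected number = 12 × [1 − exp(−h × days)].

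| Median wait | 28 days | 14 days |
|---|---|---|
| 4 years | 12 × 1.32% = 0.16 | 12 × 0.66% = 0.08 |
| 5 years (assumed) | 12 × 1.06% = 0.13 | 12 × 0.53% = 0.06 |

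**4. Effect on RR if a case occurs.** RR changes only if the participant had no earlier response, surgery precedes the window, no pre-transplant draw was made, and a post-operative draw meets a criterion. One such participant moves RR by 1/12 = 8.3 points, or 1/18 = 5.6 points if all six replacements are added. For example, 6/12 = 50.0% (Clopper-Pearson 95% CI 21.1–78.9%) becomes 7/12 = 58.3% (27.7–84.8%).

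**5. Effect on DoR.** After a dose-7 stop the sample (Day 80–94) falls close to the regular follow-up Week 1 visit (Day 79–93), so it adds about one sampling interval. After a dose-6 stop it falls 66 − 29 = 37 to 80 − 29 = 51 days after the last scheduled central sample on Day 29.

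**The case against.** The strongest reply is that 7.1.1 is a wording slip with no practical reach. It never says the visit may follow surgery, it refers sites to the SoA, and Protocol 8 requires adherence to the SoA. Every version is conditional on clinical feasibility, and four other places give the pre-transplant sequence. The SAP never says that post-transplant samples count, and SAP 1.1 describes the visit as pre-transplant. A participant handled that way and still responding is already censored at a pre-transplant sample. The 30-day timing may also serve safety, since adverse-event collection changes at 30 days after last dose. Finally, naming transplantation in the estimand is a separate choice from fixing 7.1.1.

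Much of this stands. It probably is a slip, cases will be rare, and the documents give neither an offer-to-surgery interval nor a direction for any bias. Dose delays or a scheduled living-donor operation can let both timings be met.

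It does not remove the point. The feasibility clause governs whether the visit happens, not which timing applies. The SoA cross-reference concerns what to collect and does not cancel an explicit window. Nor does the SAP consequence rest on silence alone: RR uses central assessments through 26 weeks after treatment irrespective of IMP discontinuation, and the DoR definition has no stop at transplantation.

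**Conclusion.** The contradiction is real and minor. Section 7.1.1 gives an operational rule that conflicts with the rest of the plan and can replace a pre-transplant central sample with a post-transplant one that the SAP rules would use.

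The expected number of relevant transplants is roughly 0.06 to 0.16 per 12 participants. This assumes on-schedule dosing, a constant hazard, all 12 reaching dose 6, and a 4- or 5-year median wait. Protocol 2.1.1 reports considerably lower access above cPRA 99.9%, so the rate may be lower in Cohort A. Successful desensitization or a living donor could raise it, though a planned living-donor operation also makes a pre-transplant draw easier. The 8.3-point shift is a maximum per affected participant, not an expected effect.

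DoR is descriptive ("No hypothesis/significance testing will be performed"). The correction protects the reading of single cases; the primary result is not in danger.

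**What to change.** - **Protocol 7.1.1:** align the sentence with SoA footnote b, so that the E/D central cPRA and bead sample is drawn before transplantation where clinically feasible. Any safety contact at 30 days can stay.
- **SAP 4.3 and 4.4.2.1, before database lock:** add one sentence, for example: *Central samples collected after the date of transplantation are not used for RR; DoR is censored at the last pre-transplant assessment showing response.*

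The SAP sentence needs no new data, because surgery dates (SoA footnote o) and sample collection dates (already used for DoR) are recorded. It also covers a post-transplant sample from a participant who leaves during site-visit follow-up, where footnote b allows E/D within 30 days. The protocol change needs IRB/IEC approval (Protocol 10.1.1) and can be bundled with another amendment. If no participant remains on treatment, the SAP sentence alone is enough to protect RR and DoR.
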